#### **8.7.3.4. Data review**

The following data review will be conducted to confirm the certainty of the code used in the definition.

- i. To check the number of patients by each group
- ii. To check the patient information by each group
- iii. To confirm multicollinearity between covariates
- iv. To check for outliers
- v. To check the number of patients with hospitalization due to CAP by each group
- vi. To confirm the definition of hospitalization due to CAP

Statistical test will not be performed. The definition of endpoints will not be changed except for a way of identifying COVID-19 infection whose coding can be updated over time. Some codes in the code list will be updated to the latest ones.

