### 8.7.1. General considerations

If there are more than 10% of missing data within covariates, we will discuss at the timing of the Data review (refer to “Sec 5 MILESTONES”) whether to supplement the missing data or exclude them from covariates. The result of the discussion will be approved by the senior manager. The confidence coefficient for the interval estimation is set at 95%. SAS version 9.1 (SAS Institute, Cary, North Carolina) or later is used as statistical analysis software.

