#### 8.7.3.1. Primary endpoints

##### 8.7.3.1.1. HRs for hospitalization due to CAP among incident Trelegy 100 users compared to incident MITT users

To adjust covariates (refer to “8.3.3.1 Covariates”), propensity score which is defined as a probability of Trelegy 100 treatment selection conditional on observed covariates will be estimated for an individual using logistic regression. Multicollinearity will be considered when selecting covariates. By inverse probability of treatment weighted Cox models using the propensity score, the marginal HR along with 95% confidence intervals will be estimated among incident Trelegy 100 users compared to incident MITT users. Variance estimation will be calculated using robust sandwich variance method.

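### CAP counts by group are shown at the same data review that settles the remaining propensity-score covariate and missing-data choices

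*Protocol*

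**What the plan says.** Section 8.7.3.4 lists six checks for the data review. Four matter here: "To check the number of patients by each group" (item i), patient information by group (item ii), "To confirm multicollinearity between covariates" (item iii) and "To check the number of patients with hospitalization due to CAP by each group" (item v). The section then bars statistical tests and freezes the endpoint definition, apart from how COVID-19 is identified. Some codes may be brought up to date.

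Section 8.7.1 places a modelling decision at the same review: "If there are more than 10% of missing data within covariates, we will discuss at the timing of the Data review", the options being "whether to supplement the missing data or exclude them from covariates". Its control is: "The result of the discussion will be approved by the senior manager".

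Section 8.7.3.1.1 shows where the covariates are used. The marginal HR is estimated "By inverse probability of treatment weighted Cox models using the propensity score", and for the propensity model "Multicollinearity will be considered when selecting covariates".

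Section 8.3.3.1 lists all candidate covariates in advance. It says that BMI and smoking history come from hospitalization records, and section 8.9 says that both are incompletely recorded.

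**The concern.** A propensity-score analysis is credible partly because the treatment model is settled without sight of outcomes by treatment group. Here items i and v put the crude outcome contrast on the table at the review that decides whether an incomplete covariate stays in the model and that confirms the collinearity used in selecting covariates. No statement orders those decisions before item v, and no one who decides or approves is said to be kept from the counts. A bar on testing does not help, since two counts over two denominators can be read without a test.

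At stake is the primary HR of a post-approval safety study agreed with the regulator. Section 8.9 itself names lower BMI as a risk factor for pneumonia, so keeping, imputing or dropping BMI is a real confounding choice. If it is made with the crude contrast visible, the sponsor cannot later show that the contrast played no part.

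**Working it through.** **Timing and scope, side by side**

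| Step | Where placed | Covered by a safeguard in 8.7.3.4? |
|---|---|---|
| Patients and CAP cases by group | Data review, items i and v | Tests barred; counts shown |
| Endpoint definition | Data review, item vi | Yes, frozen except COVID-19 coding |
| Impute or exclude covariates with >10% missing | Data review, by 8.7.1 | No |
| Multicollinearity, used in covariate selection | Data review, item iii; 8.7.3.1.1 | No |

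**How much of the final data the review shows**

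The Protocol gives no figure on this point, so it has to be derived.

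Inputs: index dates May 22, 2019 to May 5, 2022, 1,080 days (section 8); follow-up of at most 360 days (8.1); extraction for the review Sep 17, 2022, final extraction Sep 17, 2023, end of data Apr 30, 2023 (section 5). The last index date is 135 days before the review extraction.

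Assumptions: index dates uniform, no early discontinuation, and a data lag of L days at extraction. The Protocol states no lag for the review. Its final extraction comes 140 days after the end of data, so L = 140 is taken as the upper value and L = 0 as the lower.

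For an index date j days before the last one (j = 0 to 1,079), accrued days = min(360, max(0, 135 − L + j)). The maximum total is 1,080 × 360 = 388,800.

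- L = 0: 225 index dates give 135 to 359 days, sum 225 × 247 = 55,575. The other 855 give 855 × 360 = 307,800. Total 363,375 / 388,800 = 93.5%. Complete follow-up: 855 / 1,080 = 79%.
- L = 60: 285 × 217 + 795 × 360 = 61,845 + 286,200 = 348,045, or 89.5%. Complete: 795 / 1,080 = 74%.
- L = 140 (data to Apr 30, 2022, so the last five index days are not yet in the data): 360 index dates give 0 to 359 days, sum 64,620. The other 715 give 257,400. Total 322,020 / 388,800 = 82.8%. Complete: 715 / 1,080 = 66%.

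**How precise the crude contrast would be**

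The event counts in Tables 4 and 5 reproduce as patients × rate, with one patient-year per patient: 3225 × 0.08 = 258 and 1311 × 0.08 = 104.9, printed as 105. On that basis, for incident users, with equal rates in both groups and SE of the log ratio = √(1/d1 + 1/d2):

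- Smallest case (1935 and 1311 patients, 80 per 1000, L = 140): d1 = 154.8 × 0.828 = 128 and d2 = 104.9 × 0.828 = 87. SE = 0.139, and the 95% CI factor is exp(1.96 × 0.139) = 1.31.
- Largest case (3225 and 2185 patients, 140 per 1000, L = 0): d1 = 451.5 × 0.935 = 422 and d2 = 305.9 × 0.935 = 286. SE = 0.077, and the factor is 1.16.

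So even the smallest case fixes the crude ratio to within about 31% either side. Early discontinuation would lower these counts but raise the share accrued. Uptake rising over time would lower the share.

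**The case against.** The strongest reply is that the discretion is small. Every candidate covariate is listed in advance with its definition, and most are presence-or-absence flags from claims. A listed covariate can leave only because of missingness or collinearity, and neither trigger uses the outcome. Only BMI and smoking are named among the covariates as incompletely recorded. All of this stands and limits the point. It does not remove it: the trigger is free of the outcome, but the choice between imputing and dropping that follows is a judgement.

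A reader might infer that the confounder model is chosen knowing the answer. The Protocol does not support that. The review shows unadjusted counts, not the weighted HR, and person-time is not listed by name, so items i and v strictly give crude proportions. A reader might also infer that outlier handling and code lists are set with outcomes in view. The text says only that outliers are checked and that some codes are updated to current ones.

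The unseen SAP may hold a collinearity rule, and its absence here is no finding. But the Protocol itself schedules the missing-data decision at the review, so an earlier lock in the SAP would conflict with 8.7.1.

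Two practical objections remain. Group sizes come from a sales forecast, so event counts per group help to check feasibility. And the sponsor receives the database before passing it to the CRO (8.7), so pooling one table blinds nobody. Both are fair. They favour a dated lock, and neither justifies leaving the order of steps open.

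**Conclusion.** The point holds as a matter of procedure. The Protocol lets the remaining choices about pre-listed covariates in the primary model be made with crude CAP counts by group in view, on about 83% to 94% of the base-case person-time. That range rests on uniform index dates, no early discontinuation and a lag between 140 and 0 days. The upper end should not be quoted alone, because it needs zero lag.

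No effect on the conclusion is demonstrated. How far the HR would move if BMI or smoking were dropped cannot be derived from the Protocol. With the threshold at HR > 3, Table 1 gives 0.0% to 0.2% probability of crossing it at a true HR of 2, so the choice could change that verdict mainly if the estimate lies near 3. It would affect the reported HR and its interval in any case. This is a worthwhile, cheap improvement and not a flaw that invalidates the analysis.

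**What to change.** Make one of two changes. Either show item v in 8.7.3.4 pooled over both groups, or add a sentence to 8.7.1 and 8.7.3.4 stating that the propensity-score covariates and the missing-data method are fixed in a dated document before any CAP count by group is produced. The second is the firmer, because it leaves a record of the order of steps even though the sponsor holds the data.

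The stated purpose of the review, confirming the codes, is still met, since pooled CAP counts serve it and covariates can still be inspected by group. The cost is one changed table or one sentence, plus the small loss that event counts per group cannot be checked until those choices are locked. No design figure changes.

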## 8.8. Quality Control and Quality Assurance

The analysis for this study will be outsourced to CRO. Standard operating procedure (SOP) for analysis will be created between GSK and CRO. Based on the SOP, double programming will be performed independently within CRO and quality control (QC) records will be created. The results and QC documents will be sent to GSK as soon as QC is complete. GSK analyst will confirm that the results are correct and record them.

## 8.9. Limitations of Research Methods

This study uses MDV database which consists of hospital data, and thus only patient data in the hospitals included in MDV database are available. If a patient is treated in hospitals outside of MDV database, treatment records are not available. In MDV database, data can be extracted from health insurance claims and DPCs, but some key data (including smoking history, BMI) are not recorded completely. Based on these characteristics of MDV database, there are some limitations listed below:

- Outcome:
  - It is possible that some pneumonia events requiring hospitalization are recorded outside of DPCs, resulting in underestimation of the outcome measure. If pneumonia requiring hospitalization is treated in hospitals outside of MDV database, such data are not available and outcome measure is underestimated.
  - If data in DPC disease segment #21 (disease which triggered the hospitalization) are incorrect, occurrence of CAP will be overestimated or underestimated.
  - Pneumonia identified by only ICD-10 codes may be overestimated. Addition of prescription of antibiotics and imaging diagnosis to the outcome definition can increase the accuracy, but still there may be some overestimation.
- Risk factors for pneumonia:
  - Old age, lower % predicted forced expiratory volume in 1 second (FEV1), history of COPD exacerbations, worse Medical Research Council (MRC) dyspnea score and lower BMI were treatment-independent risk factors for pneumonia. In MDC database, data of lung function and respiratory symptoms are not available, and BMI data are only partially available.
- Exposure:
  - The reason (e.g., transfer, death) is unknown when Trelegy 100 or MITT prescription records are no longer available after the index date if a patient is treated in hospitals outside of the database. In MDV database, there are no records of the reasons for change in prescription. Dosage information is not available for inhaled drugs, and the estimated daily dose and prescription period could be different from the actual ones.
  - In MDV database, treatment adherence data are not available, and the estimated exposure period could be different from the actual one.
- Study population:
  - At least one record before the look-back period is required to secure patients records throughout the look-back period, but still there could be some missing data during the look-back period, for example, lack of treatment records in hospitals outside of MDV database.
- Others:
  - Some key data are not available including:
    - Medical history or comorbidities in the look-back period treated at hospitals outside of the

- database
- Pneumonia treatment in the look-back period at hospitals outside of the database.

The results from this study should be carefully interpreted and generalized, however if the above limitations affect both Trelegy 100 and MITT groups to a similar extent, negative impact on the internal validity of the study could be minimum.

### **8.9.1. Study closure/uninterpretability of results**

This study will be conducted in accordance with “Sec 5 MILESTONES”. If this study is terminated prematurely, GSK will determine the study closure in consultation with PMDA.

### **8.10. Other Aspects**

Not Applicable

## **9. PROTECTION OF HUMAN SUBJECTS**

### **9.1. Ethical Approval and Subject Consent**

No direct subject contact or primary collection of individual human data (IHD) will occur in this study. This study will use existing, fully de-identified data and the subject(s) cannot be identified, directly or through identifiers. Prior to the start of analysis, GSK will ask the ethics committee to review the study protocol.

### **9.2. Subject Confidentiality**

No direct subject contact or collection of personally identifiable information will occur in compliance with all applicable laws regarding subject privacy. Study results will be in tabular form and aggregate analyses that omit subject identification. Any publications and reports will not include subject identifiers.

## **10. LEGAL BASIS FOR PROCESSING INDIVIDUAL HUMAN DATA**

This study will comply with all applicable laws regarding subject privacy. No direct subject contact or primary collection of IHD will occur. This study will be conducted under Good Post-marketing Study Practice (GPSP), therefore informed consent, ethics committee or IRB approval are not mandatory required. Any publications and reports will not include subject identifiers.

The authors confirm that study data is IHD not owned by GSK, but that the proposed use of the IHD aligns with the ‘purpose of use’ outlined in the source contract and/or the terms and conditions of use of the data source and will it comply with any specified prohibitions of use.

## **11. MANAGEMENT AND REPORTING OF ADVERSE EVENTS/ADVERSE REACTIONS**

There is no potential to collect serious and non-serious adverse events (AEs), pregnancy exposures, or incidents related to any GSK product during the conduct of this research, as the minimum criteria needed to report AEs, pregnancy exposures, and incidents are not present in the data source. Further, as the research utilises existing data sources of anonymised patient data, the minimum criteria needed to report serious and non-serious AEs, pregnancy exposures, and other incidents related to a GSK product are not present in the data and thus there is no potential for reporting of AEs, pregnancy exposures and other incidents in this study.

## **12. PLANS FOR DISSEMINATING AND COMMUNICATING STUDY RESULTS**

We plan to publish the results of our study by the methods of presenting conferences and papers. The study results will be submitted for publication in a suitable peer-reviewed journal and presented at relevant conferences or meetings where possible.

## **ANNEX 1. LIST OF STAND-ALONE DOCUMENTS**

The following documents are the stand-alone documents for this study. The versions of these documents will be managed individually.

- Statistical analysis plan
- Table, figure and listing shells
- Code list

## **ANNEX 2. PVP ELEMENTS AND REQUIREMENTS TABLE**

Not Applicable

### **ANNEX 3: RETENTION OF RECORDS**

Implement appropriately according to GPSP Operating Procedures.
